### 10.4.2 Incomplete Treatments

If a subject's surgical treatment is started but discontinued due to complications or other reasons, every effort must be made to keep the subject in the study and to continue with the study required visits. For these subjects, appropriate follow-up assessments as per standard of care (including at minimum, AEs, slit lamp examination, UCDVA, manifest refraction, and BCDVA) should be conducted and collected. If the subject is not willing to complete all required follow-up visits, then document in the chart and exit the subject according to Section 10.4.3. See Section 11.6 for additional instructions for any adverse events.

*Note:* If drops are given for surgical treatment, but no laser procedure started and the surgery needs to be rescheduled, then reschedule surgery within the protocol defined visit window or follow rescreening instructions in Section 8.3.

*Note:* Please inform the Sponsor as soon as possible when an incomplete treatment occurs in order to discuss and confirm proper reporting and follow-up.

### 10.4.3 Discontinuations

Discontinued subjects are individuals who voluntarily withdraw or are withdrawn from the study by the Investigator after the surgical procedure (eye drops given for flap creation), has begun.

Subjects may discontinue from study or study treatment at any time for any reason. Subjects may also be discontinued from study treatment at any time if, in the opinion of the Investigator, continued treatment poses a risk to their health.

For subjects discontinuing from the study after treatment, the Investigator must complete all Early Exit procedures according to Table 3-1, Schedule of Study Procedures and Assessments, if the subject is willing and able, and if in the opinion of the Investigator it is safe for the subject to do so.

The Investigator must document the reason for study or treatment discontinuation in the subject's chart.

To ensure the safety of all subjects who discontinue early, Investigators must assess each subject and, if necessary, advise them of any therapies and/or medical procedures that may be needed to maintain their health.

Subject numbers of discontinued subjects must not be re-used.

## 10.5 Clinical Study Termination

The Study Sponsor reserves the right to close the investigational site or terminate the study in its entirety at any time.

If the clinical study is prematurely terminated or suspended by the Study Sponsor:

- The Study Sponsor must:
  - Immediately notify the Investigator(s) and subsequently provide instructions for study termination.
  - Inform the Investigator and the regulatory authorities of the termination/suspension and the reason(s) for the termination/suspension.
- The Investigator must:
  - Promptly notify the IRB/IEC of the termination or suspension and of the reasons.
  - Provide subjects with recommendations for poststudy treatment options as needed.

The Investigator may terminate the site's participation in the study for reasonable cause.

### 10.5.1 Follow-Up of Subjects After Study Participation Has Ended

Following this study, the subject will return to their eye care professional for their routine eye care. In cases where a subject has a continuing adverse event at the time of study completion, see Section 11.6.

## 10.6 Contingency Measures

To overcome challenges that may arise during unexpected events which could interrupt the conduct of the trial as planned (eg, natural disasters or a public health emergency), contingency measures may be implemented. The intent of contingency measures would be to

[figure not shown]
address the care of enrolled subjects during such unexpected events. It is not expected that contingency measures would affect study design; however, if necessary, the protocol would be amended accordingly. Written notification describing these contingency measures will be provided to the IRB and other regulatory agencies, as applicable. During such events, Investigators must continue to use medical judgement in the care of subjects and follow national and local guidance as well as IRB reporting requirements. Additional information can be found in the MOP.

## **11 ADVERSE EVENTS AND DEVICE DEFICIENCIES**

### **11.1 General Information**

An AE is any untoward medical occurrence, unintended disease or injury, or untoward clinical signs (including abnormal laboratory findings) in subjects, users, or other persons, whether or not related to the investigational medical device (test product). Refer to the Glossary of Terms and figures below for categories of AEs and SAEs.

**Figure 11–1 Categorization of All Adverse Events**

\*In this study, only AE related to the investigational product/device (ie, WaveLight EX500 excimer laser system) is considered as device related ADE.

### **Specific Events Relevant to this Protocol**

In addition to reporting all AEs (serious and non-serious) meeting the definitions, the Investigator must report any occurrence of the following as an ocular SAE:

- Diffuse lamellar keratitis (Grade 3 or above)
- Corneal infiltrate or ulcer

- Any persistent corneal epithelial defect at one month or later
- Corneal edema at 1 month or later (specify flap or bed)
- Epithelium in the interface with loss of 2 lines (10 letters) or more BCDVA
- Miscreated flap (lost, incomplete, too thin)
- Melting of the flap
- IOP with increase of > 10 mmHg above baseline on two consecutive examinations or an IOP greater than 30 mmHg on two consecutive examinations
- Haze beyond 6 months with loss of 2 lines or greater ( $\geq$  10 letters ETDRS) of BCDVA
- Decrease in BCDVA of greater than or equal to 2 lines ( $\geq$  10 letters ETDRS) not due to irregular astigmatism as shown by rigid contact lens refraction at 3 months or later
- Retinal detachment
- Retinal vascular accidents
- Ocular penetration
- Any other vision-threatening event

The Investigator must also report the following ocular AEs:

- Diffuse lamellar keratitis (Grade 2 or less)
- Corneal edema between one week and 1 month after the procedure
- Peripheral corneal epithelial defect at 1 month or later (location of the defect to be identified as on, off, or across the flap)
- Epithelium in the interface
- Foreign body sensation at 1 month or later
- Pain at 1 month or later
- Ghost/double images in the operative eye
- Flap is not of the size and shape as initially intended or resultant flap is misaligned

AEs that occur in association with a device that is used in conjunction with FS200 will be reported separately from those occurring with EX500.

This list is consistent with the categories provided in ANSI Z80.11 2012(R2017). Any other potentially sight-threatening event may also be considered serious based on the judgment of the Investigator and should be reported appropriately as delineated in Section 11.3.

### ***Device Deficiencies***

A device deficiency may or may not be associated with subject harm (ie, ADE or SADE); however, not all ADEs or SADEs are due to a device deficiency. The Investigator should determine the applicable category for the identified or suspect device deficiency and report any patient harm separately. Examples of device deficiencies include the following:

- Calibration issue: Error in or Unable to calibrate laser
- Computer software issue or system error message
- Defective component
- Detachment of device or device component
- Device breakage (eg, joystick)
- Device emits odor (eg, gas leak, and smoke)
- Failure of laser firing
- Failure to meet product specifications (eg, incorrect laser assembly)
- Failure to transmit record
- Foreign material present in device
- Image display error or failure to display
- Incorrect laser output energy
- Instructions difficult to understand/follow
- Mechanical issues (eg, failure to focus, align, track, position, or unintended system motion)
- Power issue: Equipment will not power on; power loss; or intermittent connection
- Other events that may meet the definition of device deficiency

## 11.2 Monitoring for Adverse Events

At each visit, after the subject has had the opportunity to spontaneously mention any problems, the Investigator should inquire about AEs by asking the standard questions shown below and report as applicable:

- “Have you had any health problems since your last study visit?”
- “Have there been any changes in the medicines you take since your last study visit?”

In addition, changes in *any protocol-specific parameters and/or questionnaires* evaluated during the study are to be reviewed by the Investigator. Any untoward (unfavorable and unintended) change in *a protocol-specific parameter or questionnaire response* that is clinically relevant, in the opinion of the Investigator, is to be reported as an AE. These clinically relevant changes will be reported regardless of causality.

## 11.3 Procedures for Recording and Reporting

AEs are collected from the time of informed consent. Any pre-existing medical conditions or signs/symptoms present in a subject prior to the start of the study (ie, before informed consent is signed) are not considered AEs in the study and should be recorded in the Medical History section of the eCRF.

In addition, dry eye, superficial punctate keratitis, and optical visual disturbances (eg, glare, halo, and starburst) are examples of early postoperative findings that are typically observed following kerato-refractive surgery. These are not considered AEs if they can be reasonably expected to resolve within 6 months and not result in any untoward long term visual outcome impact. However, based on the Investigator’s medical judgment, signs and symptoms of dry eye and ocular visual disturbances prior to 6 months, or persisting beyond 6 months post kerato-refractive surgery, may be considered an AE.

For each recorded event, the ADEs and SAEs documentation must include: date of occurrence, severity, treatment (if applicable), outcome, and assessments of the seriousness and causality. In addition, the Investigator must document all device deficiencies reported or observed with test and control products on the Device Deficiency eCRF. The site must submit all available information on ADEs, SAEs, and device deficiencies to the Study Sponsor immediately as follows:

- ADEs or SAEs are documented on the *Serious Adverse Event and Adverse Device Effect* eCRF within 24 hours of the Investigator’s or site’s awareness.

- Device deficiencies are documented on the *Device Deficiency* eCRF within 24 hours of the Investigator's or site's awareness.
- A printed copy of the completed *Serious Adverse Event and Adverse Device Effect* and/or *Device Deficiency* eCRF must be included with product returns.
- Additional relevant information after initial reporting must be entered into the eCRF as soon as the data become available.
- Document any changes to concomitant medications on the appropriate eCRFs.
- Document all relevant information from Discharge Summary, Autopsy Report, Certificate of Death, etc., if applicable, in narrative section of the *Serious Adverse Event and Adverse Device Effect* eCRF.

*Note:* Should the EDC system become non-operational, the site must complete the appropriate paper *Serious Adverse Event and Adverse Device Effect* and/or *Device Deficiency* Form. The completed form is emailed to the Study Sponsor at [contact] according to the timelines outlined above; however, the reported information must be entered into the EDC system once it becomes operational.

Any AEs and device deficiencies for non-study marketed devices/products (eg, FS200, Custom Paks) will be considered and processed as spontaneous (following the postmarket vigilance procedures) and should be communicated to the device's/product's manufacturer as per local requirements.

Study Sponsor representatives may be contacted for any protocol related question and their contact information is provided in the Manual of Procedures that accompanies this protocol.

Further, depending upon the nature of the AE or device deficiency being reported, the Study Sponsor may request copies of applicable portions of the subject's medical records. The Investigator must also report all AEs and device deficiencies that could have led to a SADE according to the requirements of regulatory authorities or IRB/IEC.

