## 1 GLOSSARY OF TERMS

Names of test product(s)	Throughout this document, test product(s) will be referred to as the WaveLight EX500 excimer laser system or EX500.
Name of Control Product(s)	N/A
Adverse Device Effect (ADE)	Adverse event related to the use of an investigational medical device (investigational product) or control product. Note: This definition includes adverse events resulting from insufficient or inadequate instructions for use, deployment, implantation, installation, or operation; any malfunction; and use error or intentional misuse of the investigational medical device (investigational product) or control product.
Adverse Event (AE)	Untoward medical occurrence, unintended disease or injury, or untoward clinical signs (including abnormal laboratory findings) in subjects, users or other persons, whether or not related to the investigational medical device (investigational product). Note: This definition includes events related to the investigational medical device, comparator, or the procedures involved. For users or other persons, this definition is restricted to events related to the use of investigational medical devices (investigational product) or control product.  Requirements for reporting Adverse Events in the study can be found in Section 11.
Anticipated Serious Adverse Device Effect (ASADE)	An effect which by its nature, incidence, severity or outcome has been identified in the risk assessment.
Device Deficiency	Inadequacy of a medical device with respect to its identity, quality, durability, reliability, usability, safety, or performance. Note: This definition includes malfunctions, use errors, and inadequacy in the

	
information supplied by the manufacturer including labelling.
 
This definition includes device deficiencies related to the investigational medical device or the comparator.
 
Requirements for reporting Device Deficiencies in the study can be found in Section 11.

Enrolled Subject	Any subject who signs an informed consent form for participation in the study.
Interventional Clinical Trial	A research trial that prospectively assigns, whether randomly or not, human participants or groups of humans to one or more health-related interventions to evaluate the effects on health outcomes, and/or a research trial in which diagnostic or monitoring procedures beyond standard of care are conducted and generate outcomes for use in analysis of data.

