### ***Causality***

Related      An AE classified as related may be either definitely related or possibly related where a direct cause and effect relationship with the medical device or study procedure has not been demonstrated, but there is a reasonable possibility that the AE was caused by the medical device or study procedure.

Not Related    An AE classified as not related may either be definitely unrelated or simply unlikely to be related (ie, there are other more likely causes for the AE).

The Study Sponsor will assess the AEs and may upgrade the Investigator's assessment of seriousness and/or causality. The Study Sponsor will notify the Investigator of any AEs that is upgraded from non-serious to serious or from unrelated to related.

Furthermore, the Study Sponsor shall promptly conduct an evaluation of any unanticipated adverse device effect, including anticipated adverse events that occur in unanticipated severity or frequency. The results of this evaluation will be reported to the FDA, the IRB, and participating Investigators within 10 working days upon receiving notification of the effect.

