### **12.7.1 Analysis of Primary Safety Endpoint(s)**

In order to assess safety of the WaveLight EX500 excimer laser system for the correction of hyperopia with and without astigmatism, the following primary safety endpoint is defined:

- Percentage of eyes experiencing ocular adverse events

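### Protocol 11.3 makes AE recording optional for dry eye and visual disturbance that outlast 6 months, so the sole primary safety percentage can be understated and can differ by site

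*Protocol*

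**What the plan says.** Protocol 11.3 names dry eye, SPK and optical visual disturbances such as glare, halo and starburst as typical early postoperative findings. It exempts them on a condition: "These are not considered AEs if they can be reasonably expected to resolve within 6 months", and provided there is no untoward long-term effect on vision. The next sentence leaves two situations to the investigator's medical judgement: dry eye and visual disturbances before 6 months, and those "persisting beyond 6 months post kerato-refractive surgery, may be considered an AE". SPK is in the exemption but is not named in that second sentence.

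Three other parts of the protocol bear on this:

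- The glossary, repeated in Section 11.1, defines an AE broadly: "Untoward medical occurrence, unintended disease or injury, or untoward clinical signs", whether or not related to the device.
- The list of specific events under Section 11.1 includes, among the ocular AEs that must be reported, "Ghost/double images in the operative eye", with no time limit. Dry eye, glare, halo and starburst are not on the list.
- Section 11.2 says that an untoward change in a study parameter or questionnaire response "that is clinically relevant, in the opinion of the Investigator, is to be reported as an AE".

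The primary safety endpoint in Section 12.7.1 is "Percentage of eyes experiencing ocular adverse events". It is summarised on the safety analysis set, with no hypothesis test.

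**The concern.** The exemption rests on an expectation that the finding will resolve within 6 months. Once it has not resolved, that expectation has failed, and the general AE definition would seem to apply. Yet the text treats findings before and after 6 months alike: either may be an AE if the investigator so judges. The 6-month limit then does no work, and no grade, duration or questionnaire threshold replaces it.

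This matters because the only primary safety endpoint is built from recorded AEs. An eye with persistent dry eye or halo that is not recorded, and that has no other ocular AE, counts as free of ocular AEs. Two sites with the same outcomes could report different percentages, and everyone is unmasked. The percentage is intended to support a registration application, where lasting effects are of most interest.

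**Working it through.** **Inputs**

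- Planned treated eyes: about 60, from 30 subjects (Protocol Section 3).
- Sites: about 4 (Protocol Section 8).
- Masking: none (Protocol 9.4).
- Expected rate, target or margin for the safety endpoint: none stated. There is no plan figure to reproduce.

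**Step 1. The texts side by side.** A finding present after 6 months falls outside the exemption by the exemption's own condition. It fits the general AE definition. The sentence that follows the exemption nevertheless makes recording permissive for dry eye and visual disturbance. For SPK it says nothing, so a reader has to infer a rule from the general definition.

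**Step 2. Is it corrected further on?** SAP 5.3.1 summarises ocular AEs and, in the text available, adds no rule for persistent findings. The sponsor's review may upgrade the investigator's "assessment of seriousness and/or causality"; it has no stated power to turn an unrecorded finding into an AE. Nothing visible closes the gap.

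**Step 3. Size per eye.** On 60 eyes, one eye not counted moves the percentage by 100/60 = 1.67 points. A bilateral case moves it by 200/60 = 3.33 points. Both are upper limits, because an eye already counted for another ocular AE changes nothing.

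**Step 4. Illustration, on assumed rates only.** Let *a* be the share of eyes with some other ocular AE, *q* the share with a finding persisting beyond 6 months, and *r* the share of those that are recorded. Assume *a* and *q* are independent. Then

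recorded percentage = 1 − (1 − a)(1 − q·r)

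shortfall against full recording = (1 − a)·q·(1 − r)

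With *a* = 10%:

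| q | all recorded | none recorded | shortfall |
|---|---|---|---|
| 5% | 1 − 0.90 × 0.95 = 14.5% | 10% | 4.5 points |
| 10% | 1 − 0.90 × 0.90 = 19.0% | 10% | 9.0 points |
| 20% | 1 − 0.90 × 0.80 = 28.0% | 10% | 18.0 points |

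If half are recorded, the shortfalls halve. With none recorded, over *a* from 5% to 20% and *q* from 5% to 30%, the shortfall runs from 0.80 × 0.05 = 4.0 points to 0.95 × 0.30 = 28.5 points. The width of that range shows how little the documents pin down.

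**Step 5. Site differences, same assumptions.** With *a* = 10% and *q* = 20%, suppose two of four equal-sized sites record every persistent finding and two record none. The first two would show 28% and the others 10%, for identical outcomes. The pooled figure would be (28 + 10)/2 = 19%, against 28% under a uniform rule.

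**The case against.** The strongest reply is that the exemption ends by its own terms, so a persistent finding reverts to the general definition, and that medical judgement is not the same as free choice. That is a reasonable reading. The permissive sentence is still the only one that speaks directly to dry eye and visual disturbance after 6 months, and a site could follow it in good faith.

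A reader might infer several stronger points that the documents do not support:

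- *That 11.3 contradicts 11.2.* It does not. The duty in 11.2 applies to a change that is "clinically relevant, in the opinion of the Investigator, is to be reported as an AE", so both sections rest on the investigator's opinion.
- *That 11.3 contradicts the mandatory list in 11.1.* The overlap is confined to ghost or double images, which could also be called a visual disturbance. A precedence statement settles it.
- *That lasting effects as a whole drop out.* They do not. Foreign body sensation and pain at 1 month or later must be reported, as must a loss of 2 lines or more of best corrected acuity at 3 months or later that is not due to irregular astigmatism.
- *That the discretion always lowers the rate.* The same sentence lets earlier findings be counted, which raises it. The downward direction holds only for persistent findings, against a rule that counts them all.
- *That the percentage will vary by site, or is understated by a known amount.* It can vary, but nothing shows that it will. No rate is given, and dry eye is a named example under the exclusion criteria, which may lower the frequency after surgery.

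It also stands that some of the information survives outside the AE count. SAP 5.3.12 tabulates abnormal slit-lamp findings by visit, and patient-reported outcome is a listed safety assessment. The manual of procedures and eCRF guidelines, to which the schedule refers for AE collection, are not available here and may narrow the discretion. A rule that defines a primary endpoint still belongs in the protocol or SAP.

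**Conclusion.** The point holds as a gap in the definition of the primary safety endpoint. Section 11.3 sits poorly with its own 6-month premise and with the general AE definition, and it gives no explicit rule for persistent SPK. The reported percentage of eyes with an ocular AE can be understated for persistent findings, and can differ by site through recording habit.

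The only size that follows from the documents is up to 1.67 points per unrecorded eye, or 3.33 per bilateral case, on about 60 eyes. The figures of 4.5 to 18 points rest on assumed rates (10% other ocular AEs, 5% to 20% persistent findings, none recorded, independence) and should not be cited as estimates.

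A reader might conclude that the study's safety decision is at risk. It is not: the endpoint has no target and no test, so only the reported figure and its interpretation are affected. This is a worthwhile, inexpensive clarification.

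**What to change.** In Protocol 11.3, replace the permissive wording for persistent findings with one rule. Dry eye, SPK or visual disturbance that is new or worse than the preoperative record, and still present after 6 months (at the 9- or 12-month visit), is recorded as an ocular AE. Severity and relatedness stay with the investigator. Keep judgement for findings before 6 months. State that the list of specific events in Section 11.1 takes precedence over this paragraph, and align the eCRF guidelines.

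Alternatively or in addition, add to SAP 5.3.1 a sensitivity summary of the primary safety percentage that also counts every eye with such a finding in the slit-lamp and patient-reported data, whatever its AE status.

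No visit is added: slit-lamp examination is already scheduled at screening and at both late visits. The text available does not show when patient-reported outcomes are collected, so the sponsor should confirm that they cover the preoperative and late visits before relying on them for symptoms. The cost is a change of wording and a somewhat higher reported ocular AE percentage that will include some mild findings. Showing severity beside the percentage would let readers see that.
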